Appendix 2 Response Evaluation Criteria in Solid Tumors (RECIST Criteria)

The RECIST criteria should be used to assess response to treatment. Only patients with measurable disease should be entered in the study. Measurable disease is defined as the presence of one lesion that can be accurately measured in at least one dimension (longest diameter to be recorded) as ≥ 2.0 cm with conventional techniques (or as ≥ 1.0 cm by spiral CT). Evaluable lesions should be followed for the assessment of response. Non-measurable lesions include bone lesions, leptomeningeal disease, ascites, pleural/pericardial effusion, lymphangitic carcinomatosis, abdominal masses that are not confirmed by CT, and cystic lesions.

All measurable lesions, up to a maximum of 5 lesions per organ and 10 lesions in total, representative of all involved organs, should be identified as target lesions and recorded and measured at baseline. A sum of the longest diameter for all target lesions will be calculated and reported as the baseline sum longest diameter. The baseline sum longest diameter will be used as the reference by which to characterize the objective tumor response.

- Complete response (CR)
Disappearance of all evidence of tumor for at least two cycles of therapy. Tumor markers must be normal.
- Partial response
At least a 30% decrease in the sum of the longest diameter of target lesions, taking as reference the baseline sum longest diameter.
- Stable disease (SD)
Neither sufficient shrinkage to qualify for partial response nor sufficient increase to qualify for progressive disease, taking as reference the smallest sum longest diameter since the treatment started.
- Progressive disease (PD)
At least a 20% increase in the sum of the longest diameter of target lesions, taking as reference the smallest sum longest diameter recorded since the beginning of treatment or the appearance of one or more new lesions.
- Clinical progressive disease
Patients, who in the opinion of the treating physician investigator have had a substantial decline in their performance status and have clinical evidence of progressive disease may be classified as having progressive disease.

**Appendix 3 National Cancer Institute Common Toxicity Criteria
for Adverse Events**

Version 4 of the NCI-CTC-AE can be obtained from:

<http://evs.nci.nih.gov/ftp1/CTCAE/About.html>

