5.6.5 Tumor and Response Evaluations

Patients will undergo tumor assessments at baseline and every 8 weeks in all cohorts assessed, regardless of dose delays, until radiographic disease progression per RECIST v1.1 or (for atezolizumab treated patients who continue treatment after radiographic disease progression) loss of clinical benefit as determined by the investigator. Thus, tumor assessments are to continue according to schedule in patients who discontinue treatment for reasons other than disease progression or loss of clinical benefit, even if they start new anti-cancer therapy. At the investigator's discretion, tumor assessments may be repeated at any time if progressive disease is suspected.

All measurable and evaluable lesions should be assessed and documented at screening. Tumor assessments performed as standard of care prior to obtaining informed consent and within 28 days prior to initiation of study treatment do not have to be repeated at screening.

Cross sectional imaging will be performed with either contrast enhanced CT or MRI. RECIST 1.1 criteria will be used to determine disease response.

If a CT scan for tumor assessment is performed in a positron emission tomography (PET)/CT scanner, the CT acquisition must be consistent with the standards for a full contrast diagnostic CT scan.

All measurable and evaluable lesions should be re assessed at each subsequent tumor evaluation. The same radiographic procedures used to assess disease sites at screening should be used for subsequent tumor assessments (e.g., the same contrast protocol for CT scans).

Response will be assessed by a blinded radiologist at the MD Anderson Quantitative Imaging Analysis Core using RECIST v1.1 (see Appendix 2) and immune-modified RECIST (see Appendix 5). Assessments should be performed by the same evaluator, if possible, to ensure internal consistency across visits. Results must be reviewed by the investigator before dosing at the next cycle.

For cutaneous squamous cell carcinoma, since “surgery (preferable) or definitive radiation therapy (with or without radiosensitizing agent)” is allowed for patients after initial response, such a definitive local therapy can only be performed after at least 1 tumor assessment.

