Appendix 4 Immune-Modified Response Evaluation Criteria in Solid Tumors (Immune-Modified RECIST)

Conventional response criteria may not be adequate to characterize the anti-tumor activity of immunotherapeutic agents like atezolizumab, which can produce delayed responses that may be preceded by initial apparent radiographic progression, including the appearance of new lesions. Therefore, immune-modified response criteria have been developed to incorporate new lesions into the assessment of total tumor burden and allow radiographic progression to be confirmed at a subsequent assessment. Immune-modified Response Evaluation Criteria in Solid Tumors (RECIST), as described within this appendix, were adapted from RECIST, Version 1.1 (v1.1) (Eisenhauer et al 2009), in the same manner that immune-related response criteria were adapted from WHO criteria (Wolchok et al. 2009) and RECIST v1.0 (Nishino et al. 2014). When not otherwise specified, RECIST v1.1 conventions will apply. Differences between immune-modified RECIST and RECIST v1.1 are summarized in Table 1.

Table 1 Comparison of RECIST v1.1 and Immune-Modified RECIST

	RECIST v1.1	Immune-Modified RECIST
Measurable new lesions	Always represent progression	Incorporated into the total tumor burden ^a and followed
Non-measurable new lesions	Always represent progression	Do not represent progression, but preclude CR
Non-target lesions	Contribute to defining CR, PR, SD, and PD	Contribute to defining CR only
CR	Disappearance of all lesions	Disappearance of all lesions
PR	≥30% decrease in sum of diameters of target lesions, in the absence of CR, new lesions, and unequivocal progression in non-target lesions	≥30% decrease in tumor burden, ^a in the absence of CR
PD	≥20% increase in sum of diameters of target lesions, unequivocal progression in non-target lesions, and/or appearance of new lesions	≥20% increase in tumor burden ^a
SD	Neither sufficient shrinkage to qualify for CR or PR nor sufficient increase to qualify for PD	Neither sufficient shrinkage to qualify for CR or PR nor sufficient increase to qualify for PD

CR=complete response; PD=progressive disease; PR=partial response; RECIST=Response Evaluation Criteria in Solid Tumors; SD=stable disease.

^a Tumor burden is the sum of diameters of target lesions and measurable new lesions.

TUMOR MEASURABILITY

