At baseline, tumor lesions/lymph nodes will be categorized as measurable or non-measurable as described below. All measurable and non-measurable lesions should be assessed at screening and at subsequent protocol-specified tumor assessment timepoints. Additional assessments may be performed as clinically indicated for suspicion of progression.

DEFINITION OF MEASURABLE LESIONS

Tumor Lesions

Tumor lesions must be accurately measured in at least one dimension (longest diameter in the plane of measurement is to be recorded) with a minimum size as follows:

10 mm by computed tomography (CT) or magnetic resonance imaging (MRI) scan (CT/MRI scan slice thickness/interval ≤ 5 mm)

10-mm caliper measurement by clinical examination (lesions that cannot be accurately measured with calipers should be recorded as non-measurable)

20 mm by chest X-ray

Malignant Lymph Nodes

To be considered pathologically enlarged and measurable, a lymph node must be ≥ 15 mm in the short axis when assessed by CT scan (CT scan slice thickness recommended to be ≤ 5 mm). At baseline and follow-up, only the short axis will be measured and followed. Additional information on lymph node measurement is provided below (see "Identification of Target and Non-Target Lesions," "New Lesions," and "Calculation of Sum of Diameters").

DEFINITION OF NON-MEASURABLE LESIONS

Non-measurable tumor lesions encompass small lesions (longest diameter <10 mm or pathological lymph nodes with short axis ≥ 10 mm but <15 mm) as well as truly non-measurable lesions. Lesions considered truly non-measurable include leptomeningeal disease, ascites, pleural or pericardial effusion, inflammatory breast disease, lymphangitic involvement of skin or lung, peritoneal spread, and abdominal mass/abdominal organomegaly identified by physical examination that is not measurable by reproducible imaging techniques.

SPECIAL CONSIDERATIONS REGARDING LESION MEASURABILITY

Bone lesions, cystic lesions, and lesions previously treated with local therapy require particular comment, as outlined below.

Bone Lesions:

Technetium-99m bone scans, sodium fluoride positron emission tomography scans, and plain films are not considered adequate imaging techniques for measuring bone lesions. However, these techniques can be used to confirm the presence or disappearance of bone lesions.

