When more than one measurable lesion is present at baseline, all lesions up to a maximum of five lesions total (and a maximum of two lesions per organ) representative of all involved organs should be identified as target lesions and will be recorded and measured at baseline. This means that, for instances in which patients have only one or two organ sites involved, a maximum of two lesions (one site) and four lesions (two sites), respectively, will be recorded. Other lesions (albeit measurable) in those organs will be considered non-target lesions.

Target lesions should be selected on the basis of their size (lesions with the longest diameter) and be representative of all involved organs, but in addition should lend themselves to reproducible repeated measurements. It may be the case that, on occasion, the largest lesion does not lend itself to reproducible measurement, in which circumstance the next largest lesion that can be measured reproducibly should be selected.

Lymph nodes merit special mention since they are normal anatomical structures that may be visible by imaging even if not involved by tumor. As noted above, pathological nodes that are

defined as measurable and may be identified as target lesions must meet the criterion of a short axis of ≥ 15 mm by CT scan. Only the short axis of these nodes will contribute to the baseline sum. The short axis of the node is the diameter normally used by radiologists to judge if a node is involved by solid tumor. Lymph node size is normally reported as two dimensions in the plane in which the image is obtained (for CT, this is almost always the axial plane; for MRI, the plane of acquisition may be axial, sagittal, or coronal). The smaller of these measures is the short axis. For example, an abdominal node that is reported as being $20\text{ mm} \times 30\text{ mm}$ has a short axis of 20 mm and qualifies as a malignant, measurable node. In this example, 20 mm should be recorded as the node measurement. All other pathological nodes (those with short axis ≥ 10 mm but < 15 mm) should be considered non-target lesions. Nodes that have a short axis of < 10 mm are considered non-pathological and should not be recorded or followed.

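### Appendix 2, the text the blinded reader must use for the RECIST v1.1 primary endpoint, does not match the protocol's own description of v1.1, so the same scans can be a response under one and not the other

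*Combined protocol and SAP*

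**What the plan says.** Sections 3.1, 4.4.1, 5.10.2.1 and 5.10.3 all name response by RECIST v1.1 as the primary endpoint. Section 5.6.5 says who reads it and by which text: "Response will be assessed by a blinded radiologist at the MD Anderson Quantitative Imaging Analysis Core using RECIST v1.1 (see Appendix 2").

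Appendix 2 carries no version number. Its rules are:

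- **Target lesions:** "All measurable lesions, up to a maximum of 5 lesions per organ and 10 lesions in total", summed by longest diameter, with no separate rule for lymph nodes.
- **Partial response:** "At least a 30% decrease in the sum of the longest diameter of target lesions, taking as reference the baseline sum longest diameter". No further condition is given.
- **Progressive disease:** a 20% rise in the target sum or a new lesion. Non-target progression is not mentioned. A separate category lets the investigator classify progression on clinical grounds.
- **Complete response:** all evidence of tumor gone for at least two cycles, with normal tumor markers.

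Appendix 4 describes v1.1 differently. The v1.1 column of its Table 1 allows partial response only "in the absence of CR, new lesions, and unequivocal progression in non-target lesions", and it counts unequivocal non-target progression as progressive disease. Appendix 4 states that it is adapted from v1.1, that "When not otherwise specified, RECIST v1.1 conventions will apply", and that Table 1 summarizes the differences. Its body text takes as targets "all lesions up to a maximum of five lesions total (and a maximum of two lesions per organ) representative of all involved organs". For lymph nodes it says: "At baseline and follow-up, only the short axis will be measured and followed".

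**The concern.** The protocol holds two accounts of the criteria that define its only primary endpoint, and the one the reader is told to use departs from the one labelled v1.1. A reader who follows Section 5.6.5 to the letter can assign a different category from one who applies the v1.1 column, on identical images.

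The appendiceal cohort is most exposed. Section 2.9.1 names peritoneal carcinomatosis among the features of low-grade appendiceal disease. Appendix 4 puts ascites among the truly non-measurable lesions, together with "lymphangitic involvement of skin or lung, peritoneal spread, and abdominal mass/abdominal organomegaly identified by physical examination". Such disease can only be non-target there, and non-target progression is exactly what Appendix 2 leaves out. Appendix 2 lists ascites as non-measurable but does not mention peritoneal spread.

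With 20 patients per cohort, one changed call can reverse a cohort's conclusion. Two sets of rules also leave room to choose between them after the scans have been seen.

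**Working it through.** **1. The plan's own figures (Section 5.10.3).** Inputs: n = 20, null rate 0.10, alternative 0.30, one-sided 0.05, exact binomial test.

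- P(X ≥ 4 | 20, 0.10) = 0.133, above 0.05.
- P(X ≥ 5 | 20, 0.10) = 0.043, so the test rejects from 5 responders.
- P(X ≥ 5 | 20, 0.30) = 0.762, matching the stated 76%.
- The Clopper-Pearson interval for 6/20 is (0.119, 0.543), as stated.

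The design arithmetic is sound. The question is what counts as a responder.

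**2. Direct conflict: non-target progression.** Suppose the target sum falls 35%, non-target disease unequivocally progresses, and there is no new lesion.

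- Appendix 2: the fall exceeds 30% and nothing else is required, so partial response.
- Appendix 4 Table 1, v1.1 column: partial response is excluded and the category is progressive disease.

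This conflict runs one way: Appendix 2 gives more responses. New lesions make no practical difference, because Appendix 2 also counts them as progression.

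**3. Conflict by inference: number of targets and nodal axis.** Table 1's v1.1 column states neither. The inference is that Appendix 4 applies v1.1 unless it says otherwise and lists no difference on these points. Its new-lesion section also gives the 15 mm nodal short axis as a baseline target criterion under RECIST. Constructed examples, with the two largest lesions as targets under the two-per-organ rule:

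| Case | Appendix 2 | Appendix 4 rule |
|---|---|---|
| (a) Liver 50, 40, 20, 20, 20 mm to 30, 25, 20, 20, 20 mm | 150 to 115: 115/150 − 1 = −23%, SD | 90 to 55: 55/90 − 1 = −39%, PR |
| (b) Liver 32, 30, 20, 20, 20 mm to 28, 26, 8, 8, 8 mm | 122 to 78: 78/122 − 1 = −36%, PR | 62 to 54: 54/62 − 1 = −13%, SD |
| (c) Sole target node 30 × 20 mm to 24 × 13 mm | longest diameter: 24/30 − 1 = −20%, SD | short axis: 13/20 − 1 = −35%, PR |

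The call moves in both directions.

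**4. Lesser differences.** Appendix 2 requires normal tumor markers for complete response and allows clinical progression. Table 1's v1.1 column contains neither. Appendix 4 bars markers from objective evaluation and treats symptomatic deterioration as a reason for stopping therapy, not a response category. These mainly affect the split between complete and partial response, PFS, disease control and duration of response. Appendix 2 calls cystic lesions non-measurable; Appendix 4 allows cystic metastases as measurable. The 5 mm absolute increase for progression appears only in the immune-modified definition.

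**5. What misclassification would do.** The documents give no rate, so these are assumptions only, each taking error in one direction.

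- A fraction r of v1.1 non-responders scored as responders: apparent null rate 0.1 + 0.9r. For r = 1%, 2%, 5% the rate is 0.109, 0.118, 0.145, and P(X ≥ 5) is 5.9%, 7.8%, 15.3%, against 4.3%.
- A fraction s of responders missed: apparent rate 0.3(1 − s). For s = 5%, 10%, 20% the rate is 0.285, 0.27, 0.24, and power is 72%, 66%, 54%, against 76%.

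**The case against.** The endpoint is called RECIST v1.1 by name throughout, and Appendix 4 lists the published v1.1 guideline among its references. An imaging-core radiologist may well apply the standard and ignore an unversioned summary. That may happen, but it would depart from Section 5.6.5, which names Appendix 2; a plan should not depend on its reader disregarding it.

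The lesion-count and nodal rules come from the appendix that serves secondary endpoints, so attributing them to v1.1 is an inference. That stands, and the claim that calls can move in either direction rests on it. The inference is also not airtight: on the same reasoning the 5 mm rule would carry over to v1.1, yet Table 1 omits it even from the immune-modified column, where the text clearly applies it. The table is therefore not a complete list. The non-target conflict needs no inference and is enough by itself.

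The misclassification rates have no documentary source, any exact test at n = 20 has a one-patient margin, and Section 5.10.4 calls the study hypothesis-generating. All true. The rates are illustration, and the point does not depend on them.

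The wrong appendix pointers are clerical, and most fit a shift of one in the appendix numbering. Agreed; they add confusion but not weight.

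**Conclusion.** The concern holds. Followed as written, the plan can record a partial response where the protocol's own v1.1 column records progressive disease. That conflict is explicit. The conflicts over number of targets and nodal axis are well supported but inferred. One changed call is enough to turn 5/20 into 4/20, or the reverse, and with it a cohort's result. The frequency of such changes is unknown, and the error rates shown rest on assumed misclassification. The 76% power and the interval (0.119, 0.543) stand. Because the primary endpoint itself is affected, this must be corrected.

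**What to change.** Replace Appendix 2 with a single set of RECIST v1.1 rules consistent with Appendix 4:

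- at most five target lesions in total and two per organ;
- short axis for lymph nodes;
- the non-target and new-lesion conditions of Table 1's v1.1 column, for both partial response and progression;
- a statement of whether the 5 mm absolute increase applies to v1.1 progression;
- one classification of peritoneal spread and cystic lesions, used for both criteria;
- no tumor-marker or clinical-progression element in the response definitions.

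Correct the pointers: Section 4.1 cites Appendix 6 (adverse event management) for RECIST v1.1 and should cite Appendix 2. Sections 4.3.2 and 5.6.5 cite Appendix 5 (the fax coversheet) for immune-modified RECIST and should cite Appendix 4.

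The cost is an appendix amendment and, since this is already Version 7, re-scoring of any scans read under the present Appendix 2. No new imaging is needed, and the sample size, rejection boundary and power do not change.

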2.5.2.2 Efficacy

Best overall response (BOR) was assessed for 74 of 97 patients in Stages I, IA, II, and IIA. Overall 6 patients (all of whom had melanoma; 6.2%) had a confirmed partial response (PR), 28 patients (28.9%) had stable disease (SD), and 40 patients (41.2%) had progressive disease. Out of the 14 CRC patients, all patients experienced progressive disease. In Stage III of Study MEK4592g, 18 patients were accrued and BOR was assessed for 14 of 18 patients. Four patients (22.2%) had SD as their BOR, and 2 patients (11.1%) had unconfirmed tumor responses.

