5.10.3 Determination of Sample Size

The primary endpoint is best ORR (PR or CR), measured as per RECIST 1.1. Three parallel single-stage phase II trials will be conducted. A total of 60 patients will be enrolled, i.e., 20 patients in each tumor group. Considering the rareness of the disease, the patient accrual rate is approximately 1 to 2 patients per month per tumor group.

Sample size calculation

For each tumor group, we will estimate the best ORR and its exact confidence interval (CI). When the sample size is 20, and the response rate is 0.3, the two-sided 95% exact CI using the Clopper and Pearson method will be (0.119, 0.543).

For each tumor group, we will also compare its overall best response rate to the historical control based on the current literature. Let p represent the overall best response rate, we will perform independent Binomial test against $H_0: p=0.1$ for each group, with a 1-sided type I error rate of 0.05. The sample size of 20 will provide 76% power to detect an improved best ORR being 30% compared to 10%.

Analysis Plan

The primary outcome is the best ORR since the start of treatment. For each tumor group, we will estimate the best response rate and its 95% exact confidence interval using the Clopper and Pearson method. And we will assess the efficacy of the combination treatment by performing the independent binomial test comparing the best response rate versus the historical control for each tumor group. The primary efficacy analyses will include all treated patients who have received at least one dose of study treatment and have baseline tumor assessment. Patients who do not receive at least 1 dose of therapy will be replaced.

For each tumor group, median DOR and corresponding 2-sided 95% CI will be reported. The association between the best ORR and other variables will be assessed using the Fisher's exact test. Time-to-event outcomes, including progression free survival (PFS) and overall survival (OS), will be estimated using Kaplan-Meier method. The log-rank test will be performed to test the difference in time-to-event distributions between patient groups. Cox proportional hazards model may be utilized to include multiple covariates in the time-to-event analysis.

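### The primary ORR has no confirmation rule for PR, so one qualifying scan makes a responder in a 20-patient cohort where one patient can decide the test

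*Combined protocol and SAP*

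**What the plan says.** The endpoint is fixed in Section 5.10.3: "The primary outcome is the best ORR since the start of treatment", with PR or CR counting as a response. The same section sets the size, "A total of 60 patients will be enrolled, i.e., 20 patients in each tumor group", and tests each cohort separately against a 10% historical rate "with a 1-sided type I error rate of 0.05", with a stated power of 76% at a true rate of 30%. It attributes the 10% to current literature and does not say whether that rate was confirmed.

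The response definitions are in Appendix 2. PR is "At least a 30% decrease in the sum of the longest diameter of target lesions", measured from baseline. No duration and no second scan are attached to it. CR is "Disappearance of all evidence of tumor for at least two cycles of therapy", and tumor markers must be normal. The RECIST v1.1 column of the comparison table in Appendix 4 defines CR without the two-cycle condition, so the two CR definitions differ. That column has no confirmation rule for PR either.

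Section 5.6.5 schedules scans every 8 weeks, read by a blinded core radiologist. Confirmation is discussed only for progression (synopsis, Sections 4.1 and 4.3.2). The protocol does draw the distinction when it reports earlier cobimetinib data: in Section 2.5.2.2 the PRs of the earlier stages are described as confirmed, while in Stage III "2 patients (11.1%) had unconfirmed tumor responses".

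For cutaneous squamous cell carcinoma (cSCC), surgery or definitive radiation is permitted during the study, and Section 5.6.5 says "such a definitive local therapy can only be performed after at least 1 tumor assessment".

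**The concern.** A best-response endpoint over repeated scans gives each patient several chances to cross the 30% threshold once. Brief shrinkage, or measurement error in a patient who has shrunk by less than 30%, then counts as a response for good. A comparator arm would carry the same error. These cohorts have none, so any excess over 10% is read as drug effect.

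With 20 patients per cohort, the conclusion can turn on a single such case. The cSCC cohort has an extra difficulty: a patient may go to local therapy after one assessment, so the scan that would confirm or refute the response may never be done.

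**Working it through.** **Inputs**
- From Section 5.10.3: n = 20 per cohort, null 0.10, alternative 0.30, one-sided 0.05, stated power 76%.
- From Sections 5.3 and 5.6.5: 28-day cycles, scans every 8 weeks.
- Not in the documents, so assumed: f, the proportion of patients without a confirmed response who are counted as PR on one scan (2%, 3%, 5%); c, the share of a 30% unconfirmed ORR that would be confirmed (90%, 80%).

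**1. Reproduce the stated design.** Under the exact binomial, P(X ≥ 4 | 20, 0.10) = 0.133 and P(X ≥ 5 | 20, 0.10) = 0.0432, so the test rejects at 5 or more responders. Power is P(X ≥ 5 | 20, 0.30) = 0.7625, which matches the stated 76%. The Clopper-Pearson interval for 6/20 is (0.119, 0.543), which also matches.

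**2. Weight of one patient.** 5/20 gives p = 0.043 and rejects. 4/20 gives p = 0.133 and does not. Reclassifying one unconfirmed PR reverses the result.

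**3. Direction.** Every patient who meets the threshold on two successive scans also meets it on at least one. Unconfirmed best ORR is therefore never below confirmed ORR.

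**4. Does the CR rule matter?** Two cycles are 2 × 28 = 56 days, or 8 weeks, which is one scan interval. A CR that lapses sooner has still shrunk by at least 30%, so it meets the PR definition and is counted. The missing PR rule is what affects the ORR.

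**5. Type I error if the 10% null is a confirmed rate.** The apparent rate is 0.10 + 0.90f, and the error is P(X ≥ 5 | 20, apparent rate).

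| f (assumed) | Apparent rate | Type I error |
|---|---|---|
| 0 | 0.100 | 4.3% |
| 2% | 0.100 + 0.018 = 0.118 | 7.8% |
| 3% | 0.100 + 0.027 = 0.127 | 10.0% |
| 5% | 0.100 + 0.045 = 0.145 | 15.3% |

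The 5% level is passed at an apparent rate of about 10.4%, that is f of about 0.45%.

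**6. Type I error if the 10% null is an unconfirmed rate.** Like is compared with like, and the error stays at 4.3%. Testing a confirmed endpoint against such a null would be too strict. If 8 of the 10 percentage points were confirmed (assumption), P(X ≥ 5 | 20, 0.08) = 1.8%.

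**7. How f could arise (illustration).** Assume independent normal error on the percentage change, SD 10 points, two scans. A patient whose true change is −10% reaches −30% on one scan with probability 0.0228. The chance of at least one such scan is 1 − (1 − 0.0228)² = 4.5%, and of both 0.0228² = 0.05%. At a true change of −20% the one-scan probability is 0.159, giving 29% and 2.5%. With no true change and SD 10, the chance of at least one such scan is 0.27%. For the −10% patient it is 0.4% at SD 7 and 17% at SD 15. So f depends heavily on the patient mix and the SD, and the documents give neither.

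**8. Power under confirmation.** Keep the rule of 5 or more of 20. With c = 90% the rate is 0.30 × 0.90 = 0.27 and power is 66%. With c = 80% it is 0.30 × 0.80 = 0.24 and power is 54%.

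**The case against.** The strongest reply is that inflation depends on how the 10% was measured. If the historical rate counted unconfirmed responses, there is none. This stands: Section 5.10.3 does not give the basis, so the type I error figures are conditional.

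Second, Appendix 2 is silent rather than permissive. It never says that one scan suffices, and a reader might argue that naming RECIST v1.1 brings in that guideline's own conventions. The protocol does not say so. Section 5.6.5 sends the reader to Appendix 2, where one qualifying scan meets the definition. A primary endpoint should not rest on that inference in either direction.

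Third, there are controls on measurement error: a blinded core radiologist, the same evaluator where possible, and the same imaging procedures throughout. Duration of response is also a secondary endpoint, so short-lived responses would partly show. These measures make a large f less likely, but none of them confirms a response.

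Fourth, confirmation has a price. It lowers power, and it can bias the cSCC cohort downward, because a genuine responder who goes to surgery after one scan would fail the endpoint. Both points stand and have to be handled in the fix.

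A reader might also infer that the difference between the CR and PR rules itself inflates the ORR, or that the 2 of 18 unconfirmed responses in Section 2.5.2.2 measure the error to expect here. Step 4 of the working rules out the first. The second comes from a drug-interaction stage of an earlier cobimetinib study without atezolizumab. It shows that the authors know the distinction, and it is not an error rate for this trial.

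**Conclusion.** The gap is real. The primary response is not required to be confirmed, nothing elsewhere in the protocol supplies the rule, and one patient can change a cohort's conclusion. That much follows from the text and exact arithmetic alone.

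The size of any inflation does not. The rise from 4.3% to between 7.8% and 15.3% needs two things the documents do not establish: a confirmed 10% null, and a single-scan PR in 2% to 5% of non-responders. A reader might conclude that the test certainly exceeds its 5% level or that the reported ORR will certainly be too high. The documents do not support that. They support an endpoint whose possible error runs in one direction, compared with a benchmark of unstated basis. This should be settled before the analysis.

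**What to change.** 1. In Section 4.4.1, Section 5.10.3 and Appendix 2, define the primary ORR as CR or PR still met at the next scheduled 8-week scan. Report the unconfirmed ORR beside it for every cohort.
2. State in Section 5.10.3 whether the 10% historical rate is confirmed or unconfirmed, and match the tested endpoint to it.
3. Keep all treated patients in the denominator. Count patients with no second scan, including cSCC patients who go to local therapy after one assessment, as not confirmed in the primary analysis. Add a sensitivity analysis that counts those with a single-scan response as responders. Removing them would select on response.
4. Reconcile the CR definitions in Appendix 2 and Appendix 4.
5. Restate the power. The 76% holds only if 30% is the confirmed rate; step 8 of the working gives the range otherwise.

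No extra imaging is needed, since Section 5.6.5 already continues the 8-week scans in patients who stop treatment for reasons other than progression or loss of clinical benefit. The real cost is a lower ORR and lower power at n = 20. The timing of local therapy in cSCC does not have to change. The final analysis, which Section 4.2 places after full enrolment, must leave the last patient time for two scans (2 × 8 = 16 weeks).
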